## **10. TREATMENT OF SUBJECTS**

### **10.1. Description of Study Drug**

CUDC-907 mesylate is a synthetic small molecule inhibitor of HDAC and PI3K. The chemical structure of CUDC-907 integrates the hydroxamic acid moiety of HDAC inhibitors into a morpholinopyrimidine pharmacophore of PI3K inhibitors.

CUDC-907 is manufactured, labeled and packaged in accordance with Good Manufacturing Practices (GMP).

CUDC-907 mesylate oral capsules are formulated with three excipients: silicified microcrystalline cellulose (Prosolv® HD90), sodium starch glycolate (Explotab®), and magnesium stearate. The resulting dry blended mixture is filled into gelatin capsule shells.

### **10.2. Supply, Packaging and Labeling**

CUDC-907 will be supplied as gelatin capsules containing 30 mg CUDC-907 and excipients.

The capsules are packaged in high-density polyethylene bottles containing 35 capsules each, and appropriately labelled for clinical trial use as per national regulatory requirements.

### **10.3. Storage and Dispensing**

The study drug should be stored at room temperature in a secure area with access limited to the Investigator and authorized site staff.

Only subjects enrolled in the trial may receive investigational product. The investigational materials are to be prescribed only by the PI or the sub-Investigators named in FDA Form 1572. In addition, the study drug may only be dispensed by authorized personnel at the institution(s) specified on Form 1572. For self-administration, subjects may be provided with a sufficient number of capsules as are needed for 1 cycle of study drug administration.

Under no circumstances is the investigational drug to be used other than as directed within this study protocol.

### **10.4. Investigational Product Accountability**

Study drug accountability records will be maintained throughout the course of the study. The Investigator or designee will document the amount of study drug received, the amount dispensed to study subjects and the amount destroyed locally.

Unused study drug remaining at the completion of the study will be destroyed at the site per institutional standard operating procedures provided that destruction is documented.

### **10.5. Study Drug Administration**

#### **10.5.1. CUDC-907**

Subjects will receive CUDC-907 60 mg in 21-day cycles.

CUDC-907 will be administered orally at the assigned dose level and schedule, 60 mg on a 5/2 schedule.

All doses of study drug (in clinic and self-administered) will be administered with meals ( $\pm$  30 minutes) at approximately the same time each dosing day, if possible.

Dose and/or schedule intensity of CUDC-907 may be reduced per protocol due to toxicity.

In the absence of significant toxicity, each subject is expected to complete at least 1 cycle (21 days) of study treatment. However, subjects may continue to receive additional 21-day cycles of CUDC-907 treatment until disease progression has been documented or other discontinuation criteria have been met (Section 9.3.1).

### 10.5.2. Retreatment Criteria

Subjects may continue to receive 21-day cycles of study treatment until disease progression has been documented or other discontinuation criteria have been met (Section 9.3.1).

To continue dosing of CUDC-907 subjects must meet the following criteria:

- $ANC > 1,000/\mu L$ .
- Platelets  $\geq 50,000/\mu L$ .
- $AST$  and  $ALT \leq 2.5 \times ULN$ .
- Bilirubin concentration  $\leq 1.5 \times ULN$  (or  $\leq 3 ULN$  for patients with documented Gilbert's syndrome).
- Creatinine  $\leq 1.5 \times ULN$ .
- $\leq$  Grade 2 diarrhea controlled by antidiarrheal treatment.

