  - Refractory disease is defined by (a) PD during prior treatment, (b) stable disease (SD) after  $\geq$  3 cycles of prior treatment, or (c) PR after  $\geq$  6 cycles of prior treatment, or for stage II disease,  $\geq$  3 cycles of treatment and definitive involved field radiotherapy.

- For sustained PR after prior treatment, confirmation biopsy for DLBCL is preferred. An FNA may be acceptable, but if inappropriate (e.g., due to biopsy inaccessibility), the Sponsor may determine eligibility following review of imaging results and disease history.
  - For SD or PD after prior treatment, reconfirmation of DLBCL by biopsy (preferred) or FNA is recommended but not mandatory.
7. Eastern Cooperative Oncology Group (ECOG) performance status of  $\leq 2$ .
  8. Recovery to Grade 1 or baseline of any toxicity due to prior anticancer therapies (excluding alopecia).
  9. Absolute neutrophil count (ANC)  $\geq 1,000/\mu\text{L}$ ; platelets  $\geq 75,000/\mu\text{L}$ ; creatinine  $\leq 1.5 \times$  upper limit of normal (ULN) or calculated creatinine clearance  $\geq 50$  mL/minute as determined by Cockcroft-Gault (using actual body weight) or by 24-hour urine collection measurements of creatinine; aspartate aminotransferase (AST) and/or alanine aminotransferase (ALT)  $\leq 2.5 \times$  ULN; total bilirubin  $\leq 1.5 \times$  ULN or  $\leq 3$  ULN for patients with documented Gilbert's syndrome. Platelet transfusions and administration of granulocyte colony-stimulating factors to help patients meet eligibility criteria are not allowed within 1 week prior to screening complete blood count (CBC) and Cycle 1, Day 1 treatment.
  10. Women of childbearing potential must have a negative serum or urine pregnancy test (not applicable after bilateral oophorectomy)
  11. Men and women of childbearing potential and their partners must agree to use adequate birth control throughout their participation in the study and for 30 days following the last study treatment. Adequate contraception is defined as hormonal birth control, intrauterine device, double barrier method or total abstinence. Acceptable methods of contraception are described in [Table 3](#).
  12. In the Investigator's judgement, able to provide written informed consent and follow protocol requirements.

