### 10.5.3. Safety Criteria for Adjustment or Stopping CUDC-907

#### 10.5.3.1. Dose Delays and Discontinuation of CUDC-907

In the event that any of the above criteria are not met, study drug dosing must be held until the retreatment criteria are met. Treatment may then resume at the full dose of CUDC-907, as long as none of the criteria in Table 2 are met. Beyond Cycle 1, subjects held for  $> 7$  days may restart treatment after the subject has met the above criteria and following discussion and agreement between the Investigator and the Medical Monitor. Beyond Cycle 2, subjects may have study drug held for up to 7 days between the end of a cycle and initiation of another (e.g., Cycle 2 Day 21 to Cycle 3 Day 1). This hold will be at the discretion of the Investigator and after discussion and agreement between the Investigator and Medical Monitor.

Study treatment should be discontinued in the event of an unacceptable toxicity or treatment hold lasting more than 4 weeks, except in cases of clinical benefit determined by the Investigator with approval by the Sponsor Medical Monitor.

Subjects who experience a DLT-like event will be either discontinued from further study treatment or their dose will be reduced following discussion and agreement between the Investigator and the Sponsor's Medical Monitor. A DLT-like event will be defined as any of the following AEs occurring at any time:

- Non-hematological  $\geq$  Grade 3 AE, other than Grade 3 nausea or Grade 3 vomiting in subjects treated with less than optimal antiemetic therapy.
- An AE resulting in a dose delay of  $\geq$  7 consecutive days (e.g., 6 consecutive missed doses).
- Grade 4 neutropenia  $\geq$  7 days, or  $\geq$  Grade 3 neutropenia with fever  $>$  101.3°F (38.5°C) or  $\geq$  Grade 3 neutropenia with infection.
- Grade 4 thrombocytopenia  $\geq$  7 days, or  $\geq$  Grade 3 thrombocytopenia and significant bleeding.

**NOTE:** A DLT-like event excludes AEs that are clearly and incontrovertibly related to the underlying disease or extraneous factors.

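### A subject admitted on creatinine clearance with creatinine above 1.5 × ULN fails the Section 10.5.2 retreatment limit at an unchanged value and must be held (minor)

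*Combined protocol and SAP*

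**What the plan says.** **Entry.** Inclusion criterion 9 (Section 9.1, repeated in the Synopsis) offers two renal routes: creatinine no higher than 1.5 × "upper limit of normal (ULN) or calculated creatinine clearance" of at least 50 mL/min. Clearance may come from Cockcroft-Gault with actual body weight "or by 24-hour urine collection measurements of creatinine". Either route is enough.

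**Continuing.** Section 10.5.2 opens with "To continue dosing of CUDC-907 subjects must meet the following criteria". Its renal line is creatinine no higher than 1.5 × ULN and nothing more. The bilirubin line of the same list does carry its entry exception forward, with a higher limit "for patients with documented Gilbert's syndrome".

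**Consequence.** Under Section 10.5.3.1, if any criterion is not met, "study drug dosing must be held until the retreatment criteria are met". For longer holds the section says: "Beyond Cycle 1, subjects held for" more than 7 days "may restart treatment after the subject has met the above criteria and following discussion and agreement between the Investigator and the Medical Monitor". After a hold of more than 4 weeks treatment should be discontinued, "except in cases of clinical benefit determined by the Investigator with approval by the Sponsor Medical Monitor".

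**The concern.** The entry rule deliberately lets in some subjects whose creatinine is above 1.5 × ULN. The continuation rule then treats that same value as a reason to stop drug. A limit that the subject already exceeded before the first dose cannot detect an effect of the drug.

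What is at stake is the treatment of individual subjects. Someone with relapsed or refractory lymphoma, whom the protocol judged fit to be dosed, could lose drug without any toxicity. If creatinine stays where it was, the hold does not end by itself, and after 4 weeks the discontinuation rule is reached. Sites that meet the problem would have to resolve it case by case as deviations.

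**Working it through.** The plan gives no figure to reproduce here. The check has three parts: do the rules conflict, does any clause lift the hold, and can an affected subject exist?

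**1. The two renal rules side by side**

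| | Entry (9.1, no. 9) | Continue dosing (10.5.2) |
|---|---|---|
| Creatinine ≤ 1.5 × ULN | sufficient | required |
| Clearance ≥ 50 mL/min | sufficient instead | not mentioned |
| Baseline allowance | – | none |

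A subject with creatinine above 1.5 × ULN and clearance of at least 50 mL/min passes the first column and fails the second at the same value.

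**2. Clauses that might lift the hold**

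- The restart rule for holds over 7 days (10.5.3.1) still requires the criteria to be met.
- The clinical-benefit exception (10.5.3.1) is attached to discontinuation after more than 4 weeks, not to the hold.
- The return-to-baseline wording in Table 2 (10.5.3.3) concerns recovery from graded toxicities. Section 10.5.3.1 turns to Table 2 for the resumption dose only after the retreatment criteria are met.
- The Medical Monitor permission in Section 13 covers treatment or assessments not done on time, not a failed criterion.
- Section 15.4 allows a departure with the Sponsor's written agreement, reported to the IRB/IEC. This route works, but only as a deviation.

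**Timing.** Eligibility governs the first dose. Section 10.5.2 does not name the visits at which it applies. Chemistry is drawn on Cycle 1 Days 5 and 12 and on Day 1 of later cycles (Section 5.1). The hold could therefore begin in Cycle 1 if 10.5.2 is applied at those visits, and otherwise at the start of Cycle 2.

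**3. Can such a subject exist?**

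Cockcroft-Gault: clearance = (140 − age) × kg × f / (72 × Cr), with f = 1 for men and 0.85 for women. The protocol names the method without printing the formula. It gives no ULN for creatinine, so ULN is assumed: 1.0, 1.2 or 1.3 mg/dL for men and 0.9, 1.0 or 1.1 mg/dL for women. To place the subject clearly over the limit, take Cr = 1.6 × ULN. Clearance is at least 50 when age ≤ 140 − 3,600 × Cr / (kg × f), since 50 × 72 = 3,600. Oldest qualifying age in whole years:

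| Weight | Men, ULN 1.0 / 1.2 / 1.3 | Women, ULN 0.9 / 1.0 / 1.1 |
|---|---|---|
| 60 kg | 44 / 24 / none aged ≥ 18 | 38 / 27 / none aged ≥ 18 |
| 70 kg | 57 / 41 / 33 | 52 / 43 / 33 |
| 80 kg | 68 / 53 / 46 | 63 / 55 / 46 |
| 90 kg | 76 / 63 / 56 | 72 / 64 / 57 |

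Example: for a man aged 50 weighing 80 kg, (140 − 50) × 80 / 72 = 100, so clearance is 100 / Cr. At 1.92 mg/dL (1.6 × 1.2) it is 52.1 mL/min. He is eligible, and 10.5.2 then requires a hold at that same 1.92.

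Such subjects are arithmetically possible, mostly among younger or heavier people. Entry by 24-hour urine is a further route that this grid does not cover. The grid gives no frequency, because the documents contain no distribution of age, weight or creatinine.

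**The case against.** The best case for the plan is that 10.5.2 is meant as a toxicity screen. Section 9.3.1 cites it when describing unmanageable toxicity. Section 10.5.1 expects at least one completed cycle when there is no significant toxicity. Section 12.1 does not count a pre-existing condition that has not worsened as an adverse event. Read together, these suggest that nobody intended to hold a subject at a stable baseline value. That stands as evidence of intent, but none of these clauses overrides the mandatory wording of 10.5.2 and 10.5.3.1.

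A second argument is that the on-treatment list was set separately from the entry list. Platelets go from 75,000 to 50,000/µL, and the ANC limit changes from at least 1,000 to above 1,000/µL. The Gilbert's contrast therefore does not prove an oversight. A single serum-creatinine stop is also defensible for a drug with expected diarrhea and a risk of dehydration (Sections 6.3.1 and 10.6.1). This too stands in part: a stricter limit on drug can be a legitimate choice. It does not justify a limit that is already failed before dosing.

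A reader might go further and infer that these subjects can never be dosed, or that they have no way to continue. The documents support neither: the first dose falls under eligibility, and Section 15.4 leaves the deviation route open.

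**Conclusion.** The two rules conflict as written. A subject enrolled on clearance with creatinine above 1.5 × ULN must be held from the first on-treatment chemistry to which 10.5.2 is applied, whether or not creatinine has moved. Only a Sponsor-agreed deviation keeps the subject on drug. This conclusion rests on the text alone. The assumed ULNs serve only to show that such a subject can exist.

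The size cannot be computed; it may be zero. A reader might infer that the response rate or the interim decision is compromised. The documents do not support that: no endpoint definition, sample size or interim rule depends on this line, and nothing in them gives a count of affected subjects. Severity is minor.

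**What to change.** Change the creatinine line of Section 10.5.2 to:

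*Creatinine ≤ 1.5 × ULN or, for subjects enrolled with creatinine > 1.5 × ULN on the basis of creatinine clearance ≥ 50 mL/min, creatinine no more than 10% above the Cycle 1 Day 1 pre-dose value.*

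The 10% is an assumed allowance for ordinary variation, and the Medical Monitor can set another figure. Some tolerance is needed. With none, a small upward fluctuation would recreate the hold, notably for a subject who entered by 24-hour urine with a Cockcroft-Gault value below 50. Naming the Cycle 1 Day 1 value avoids doubt where it differs from screening.

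The more obvious repair, allowing dosing whenever clearance is still at least 50 mL/min, is not recommended, because it leaves too much room for a rise on drug:

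- Man aged 50, 80 kg, ULN 1.0: at 1.60 mg/dL clearance is 100 / 1.60 = 62.5. It reaches 50 at 2.00 mg/dL, a rise of 0.40 / 1.60 = 25%.
- Man aged 40, 90 kg, ULN 1.2: 100 × 90 / 72 = 125, so at 1.92 mg/dL clearance is 65.1. It reaches 50 at 2.50 mg/dL, a rise of 0.58 / 1.92 = 30%.

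**Cost.** One line, which can go into the next amendment. It uses chemistry already scheduled and needs no repeat 24-hour urine, which the Schedule of Events does not include. The few subjects admitted on clearance would keep dosing at about their entry renal function. A 10% rise could take a borderline subject slightly below 50 mL/min: the 50-year-old, 80 kg man going from 1.92 to 2.112 mg/dL falls from 52.1 to 100 / 2.112 = 47.3. Everyone else keeps the present stop. A man of the same age and weight who rises on drug from 1.0 to 1.9 mg/dL (1.9 / 1.2 = 1.58 × ULN, clearance 52.6) is still held.

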### 10.5.3. Safety Criteria for Adjustment or Stopping CUDC-907

#### 10.5.3.1. Dose Delays and Discontinuation of CUDC-907

In the event that any of the above criteria are not met, study drug dosing must be held until the retreatment criteria are met. Treatment may then resume at the full dose of CUDC-907, as long as none of the criteria in Table 2 are met. Beyond Cycle 1, subjects held for  $> 7$  days may restart treatment after the subject has met the above criteria and following discussion and agreement between the Investigator and the Medical Monitor. Beyond Cycle 2, subjects may have study drug held for up to 7 days between the end of a cycle and initiation of another (e.g., Cycle 2 Day 21 to Cycle 3 Day 1). This hold will be at the discretion of the Investigator and after discussion and agreement between the Investigator and Medical Monitor.

Study treatment should be discontinued in the event of an unacceptable toxicity or treatment hold lasting more than 4 weeks, except in cases of clinical benefit determined by the Investigator with approval by the Sponsor Medical Monitor.

Subjects who experience a DLT-like event will be either discontinued from further study treatment or their dose will be reduced following discussion and agreement between the Investigator and the Sponsor's Medical Monitor. A DLT-like event will be defined as any of the following AEs occurring at any time:

- Non-hematological  $\geq$  Grade 3 AE, other than Grade 3 nausea or Grade 3 vomiting in subjects treated with less than optimal antiemetic therapy.
- An AE resulting in a dose delay of  $\geq$  7 consecutive days (e.g., 6 consecutive missed doses).
- Grade 4 neutropenia  $\geq$  7 days, or  $\geq$  Grade 3 neutropenia with fever  $>$  101.3°F (38.5°C) or  $\geq$  Grade 3 neutropenia with infection.
- Grade 4 thrombocytopenia  $\geq$  7 days, or  $\geq$  Grade 3 thrombocytopenia and significant bleeding.

**NOTE:** A DLT-like event excludes AEs that are clearly and incontrovertibly related to the underlying disease or extraneous factors.

### 10.5.3.2. CUDC-907 Dose Reductions

**Table 1: Dose Reduction Steps for CUDC-907**

Reduction Steps:	Schedule	Dose
Starting dose	5/2	60 mg
Dose Reductions	Schedule	Dose
First dose reduction	4/3	60 mg
Second dose reduction	5/2	30 mg
Final dose reduction	4/3	30 mg

4/3 = 4 days on/3 days off; 5/2 = 5 days on/2 days off

### 10.5.3.3. Dose Adjustments for CUDC-907 Hematologic and Non-hematologic Toxicity

The administration of HDAC and PI3K inhibitors has been associated with predictable bone marrow suppression that is typically transient and reversible.

The administration of HDAC and PI3K inhibitors has also been associated with hyperglycemia. This hyperglycemia does not generally result in severe metabolic complications and typically resolves with therapeutic intervention. The treatment goal for glycemic control is fasting plasma glucose  $<$  160 mg/dL; while making every attempt to avoid hypoglycemia. Dose modifications of CUDC-907 are based on the severity of toxicities.

CUDC-907 dose adjustments for hematologic and non-hematologic toxicities are shown in [Table 2](#).

Table 2: CUDC-907 Dose Adjustments for Hematologic and Non-Hematologic Toxicities			
Thrombocytopenia	Grade 1 or 2 No change in dose	Grade 3 or 4 (platelets < 50,000/μL) Hold treatment until platelets ≥ 50,000/μL or baseline, then reduce dose to the next lower dose level (as applicable per Table 1 ).	Grade 4 thrombocytopenia requiring platelet transfusion Hold treatment until platelets ≥ 75,000/μL or baseline, then dose reduce to the next lower dose level (as applicable per Table 1 ).
Neutropenia	Grade 1 or 2 No change in dose	Grade 3 or 4 (ANC < 1,000/uL) Hold treatment until ANC ≥ 1000/μL, then reduce dose to the next lower dose level (as applicable per Table 1 ).	Grade 4 febrile (≥ 38.5° C) neutropenia Hold treatment until febrile neutropenia resolves and ANC ≥ 1000/μL or baseline, then dose reduce to the next lower dose level (as applicable per Table 1 ).
Anemia	Grade 1 or 2 No change in dose	Grade 3 or 4 (hemoglobin < 8 g/dL) Hold treatment until hemoglobin ≥ 10 g/dL or baseline then reduce dose to the next lower dose level (as applicable per Table 1 ).	Grade 4 anemia requiring transfusion Hold treatment until hemoglobin ≥ 10 g/dL or baseline, then dose reduce to the next lower dose level (as applicable per Table 1 ).
Recurrence of Grade 3 or 4 hematologic toxicity will be cause for a second dose modification. If the starting dose does not permit dose modification, then study drug will be discontinued.			
Non-hematological AEs (excluding hyperglycemia)	Grade 1 or 2 No change in dose 	Grade 3 
 
Hold treatment until resolution to ≤ Grade 1 or baseline
 
If not recovered to ≤ Grade 1 or baseline within 3 weeks, reduce to next lower dose level upon return to ≤ Grade 1 or baseline (as applicable per Table 1).
 
	Grade 4 Discontinue treatment. 
Recurrence of Grade 3 non-hematologic toxicity (excluding hyperglycemia) or inability to reduce dose (based on starting dose) will be grounds for discontinuation of study drug.			

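### After a first Grade 3 non-hematologic toxicity that recovers within 3 weeks, Section 10.5.3.1 requires reduction or discontinuation, Table 2 triggers neither, and nothing says which rule governs

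*Combined protocol and SAP*

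**What the plan says.** Two parts of Section 10.5.3 of the protocol govern the dose after a Grade 3 non-hematologic event.

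**Section 10.5.3.1.** One criterion for a DLT-like event is a non-hematological event of at least "Grade 3 AE, other than Grade 3 nausea or Grade 3 vomiting in subjects treated with less than optimal antiemetic therapy". Another is an event causing a dose delay of at least "7 consecutive days (e.g., 6 consecutive missed doses"). Either counts whenever it happens on study. A note carves out some events: "A DLT-like event excludes AEs that are clearly and incontrovertibly related to the underlying disease or extraneous factors". The consequence is stated as: "Subjects who experience a DLT-like event will be either discontinued from further study treatment or their dose will be reduced", after the investigator and the Medical Monitor agree.

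**Table 2 (Section 10.5.3.3).** The row for non-hematological events leaves out hyperglycemia, which has its own row. Its Grade 3 cell says to hold until the event is back to Grade 1 or lower or baseline, then: "If not recovered to ≤ Grade 1 or baseline within 3 weeks, reduce to next lower dose level". A recurrent Grade 3 event in this row is grounds for stopping the drug.

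Section 10.5.3.1 mentions Table 2 once, for holds due to unmet retreatment criteria: "Treatment may then resume at the full dose of CUDC-907, as long as none of the criteria in Table 2 are met".

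**The concern.** Both rules apply to a first Grade 3 event that recovers within 3 weeks, and they lead to different doses. Section 10.5.3.1 takes no account of how fast the event resolves and offers no same-dose restart. Table 2 makes reduction depend on slow recovery.

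At stake is the dose a patient goes back on after a severe toxicity. Section 6.3.1 names diarrhea and fatigue among the drug-related Grade 3 or 4 events seen in at least two Phase 1 subjects. Because Table 2 makes recurrence grounds for stopping, a same-dose restart is in effect a single rechallenge. A patient who then recurs may lose the drug without having tried a lower dose.

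There is also a smaller effect on safety data. Section 9.3.2 lists dose reductions and discontinuations due to toxicity among the inputs to the Safety Review Committee. With up to 65 sites, those counts would partly reflect which rule each site followed.

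**Working it through.** The plan gives no figure to reproduce here. The check compares the texts and then works out the doses.

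**1. Scope.** The overlap is a first Grade 3 non-hematologic event, not hyperglycemia, that recovers within 3 weeks and is not excluded from the DLT-like definition. Nausea or vomiting on inadequate antiemetics, and events clearly due to disease or extraneous causes, are excluded.

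**2. One patient under both rules.** Take a first Grade 3 fatigue or diarrhea at 60 mg 5/2, recovered on day 10 of the hold.

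| Rule | Action | Restart dose |
|---|---|---|
| Table 2, Grade 3 cell | Hold; 10 days is under 3 weeks, so no reduction | 60 mg 5/2 (implied) |
| Section 10.5.3.1 | DLT-like by grade: reduce or discontinue | 60 mg 4/3 (first step of Table 1) or none |

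Table 2 does not write out the same-dose restart. It is inferred, because reducing in every case would leave the 3-week condition with no function. The Grade 3 hematologic cells support the inference: they reduce after the hold with no time condition.

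**3. Planned dose per 21-day cycle (Table 1).**
- 60 mg 5/2: 5 × 3 = 15 doses; 15 × 60 = 900 mg (300 mg/week).
- 60 mg 4/3: 4 × 3 = 12 doses; 12 × 60 = 720 mg (240 mg/week).
- Difference: 900 − 720 = 180 mg; 180/900 = 20%.
- Discontinuation: 0 mg.

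**4. Does any text rank the rules?**
- The full-dose resumption sentence applies only to holds for unmet retreatment criteria (Section 10.5.2). Diarrhea is covered, since patients must be no worse than "Grade 2 diarrhea controlled by antidiarrheal treatment"; fatigue is not listed. Its reference to Table 2 criteria is also ambiguous. It can mean the Grade 3 column itself, which bars full dose, or the column's reduction trigger, which does not.
- Section 8.3.1 points to Section 10.5.3 as a whole and settles only Grade 4 DLT-like events.
- The clinical-benefit exception in footnote 2 of Table 2 is attached to the Grade 4 and hyperglycemia entries, not to this cell.

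**5. The delay criterion adds a second overlap.** Dosing days on 5/2 are 1–5, 8–12 and 15–19. Any 7 consecutive days contain 5 doses. Six consecutive doses always span 8 days (for example days 1–5 and 8). The criterion therefore starts at day 7 as written, or day 8 by its own example. Counting Table 2's 3 weeks (21 days) from the start of the hold, a hold of 7–21 days (or 8–21) is DLT-like by delay as well as by grade, still with no Table 2 reduction.

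**The case against.** The best reply is that a site which always reduces breaks neither text: Section 10.5.3.1 is mandatory, and Table 2 is silent on the restart dose after quick recovery. That is correct as far as it goes. A reader might infer that Table 2 expressly orders full dose, or that sites are forced to breach one rule; the documents support neither. But the always-reduce reading empties the 3-week condition, and nothing tells a site to adopt it.

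A second reply is that diarrhea, AST/ALT, bilirubin and creatinine fall under the retreatment criteria, where one natural reading of the resumption sentence already bars full dose. This stands for that reading only, and it does not reach fatigue.

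A third concerns oversight. A reader might infer that full-dose restarts go unchecked, which overstates it. Medical Monitor agreement is required for every DLT-like event, Cycle 1 included. Beyond Cycle 1, subjects held for more than 7 "days may restart treatment after the subject has met the above criteria and following discussion and agreement between the Investigator and the Medical Monitor". The first footnote to the Schedule of Events and the opening of Section 13 also require Medical Monitor permission to continue when extenuating circumstances disrupt treatment timing; whether a toxicity hold counts is arguable. What remains is that a site reading Table 2 alone could miss the DLT-like step.

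Finally, the consequences are limited. Section 6.3.1 pools Phase 1 schedules, and Section 6.1.3 reports no dose-limiting toxicities at 60 mg 5/2. The Safety Review Committee also sees Grade 3 or higher toxicity directly. All of this stands and keeps the importance modest.

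**Conclusion.** The protocol is wrong as written on this row. It is an internal inconsistency rather than a debatable design choice. For the events in scope, one rule requires reduction or discontinuation and the other implies restart at the same dose, with no order of precedence. At the starting level that is 900 mg per cycle against 720 mg (20% less) or zero.

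This rests on two assumptions: that same-dose restart is the intended meaning of Table 2's conditional reduction, and that the patient is at 60 mg 5/2 when the first event occurs. The number of patients affected cannot be stated.

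A reader might go on to infer a threat to the primary analysis or to the stopping rules. The documents do not support that: no response-rate rule and no numeric safety guideline depends on which dosing rule a site follows. The point should be fixed, at the low end of that category, because it sets a patient's dose after severe toxicity and the correction is cheap.

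**What to change.** State one action, by amendment.

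**Option 1 (DLT-like rule governs).** Reword the Table 2 Grade 3 non-hematologic cell: *hold until Grade 1 or lower or baseline; if the event is DLT-like per 10.5.3.1, then reduce to the next lower level per Table 1 or discontinue, as agreed with the Medical Monitor; otherwise reduce only if not recovered within 3 weeks*. A blanket reduction would go too far, because it would catch events that the DLT-like definition excludes.

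**Option 2 (same-dose restart is intended).** Exempt first Grade 3 non-hematologic events that recover within 3 weeks from both the grade and the delay criteria of the DLT-like definition, and write *resume at the same dose* in the cell.

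Under either option:
- Let the Section 10.5.3.1 resumption sentence permit full dose *unless Table 2 or the DLT-like rule requires reduction or discontinuation*. Naming reduction alone would omit Table 2's discontinuation rules.
- Say whether the delay criterion is 7 calendar days or 6 missed doses (8 days on 5/2).

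The change should go through IRB/IEC review before sites apply it (Sections 15.4 and 15.5), so a site letter choosing a rule ahead of the amendment is not advised.

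The cost is that review plus site retraining, with no added visits, procedures or patients. Option 1 lowers the dose for some patients who recover quickly. Option 2 keeps them at full dose after a Grade 3 event. That trade-off is the sponsor's clinical decision.
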